#### 10.3.1.1 Additional information for the Investigator in case of decision to withdraw a patient from IMP

To support the Investigator in his/her decision to withdraw a patient from IMP, it is recommended to use the maximum intensity of any IMP-related adverse events (see [Section 13.1.1.3](#)) as the basis for evaluation. If the patient reports any severe adverse events that are determined to be related to L-CsA, the Investigator should consider withdrawing the patient from IMP.

Spirometry using the **CCI** spirometer will be performed **CCI**

Patients may be evaluated in the clinic on Day 2 for further observation with administration of L-

CsA if warranted in the Investigator's opinion based upon Day-1 L-CsA administration. A reduction in the FEV1 of **CCI** associated with clinical symptoms of breathlessness or other respiratory symptoms will be considered intolerance of the IMP and grounds for discontinuation of inhalation.

#### **10.3.2 Replacement of Withdrawn Patients**

Patients withdrawn before randomization (e.g., screening failures) will be replaced until the pre-defined number of randomized patients has been reached. If a subject fails the screening process due to not meeting inclusion/exclusion criteria, a re-screening is allowed. Randomized patients will not be replaced. The eligibility of prematurely withdrawn patients for the different analysis populations will be determined in a blind data review meeting with consideration of the definition of these analysis populations provided in [Section 15.1](#).

#### **10.3.3 Follow-up of Withdrawn Patients**

Patients stopping to take study treatment but not revoking their consent will be encouraged to continue the visits planned until the scheduled end and perform all the important safety and efficacy assessment for the full duration of the study.

All patients withdrawn from the clinical trial prematurely will be followed for AEs and SAEs for a further 4 weeks. Any patient with ongoing SAEs will be followed until recovery or stabilization of the SAE.

The 4-week safety follow-up will be obsolete if a patient completes participation in the clinical trial and consents to participate in Clinical Trial BT – L-CsA – 303 – FU (BOSTON-3). In this case, safety will be continuously assessed in the scope of the follow-up clinical trial.

#### **10.3.4 Completion of Clinical Trial and Lost to Follow-up**

Patients will be considered to have completed the clinical trial if they were followed-up through Visit 9 (Week 48).

A patient will be considered lost-to-follow-up only if no contact has been established by the time the clinical trial is completed such that there is insufficient information to determine the patient's status at Visit 9 (Week 48). The Investigator should document attempts to re-establish contact with any missing patient throughout the clinical trial period. If contact with a missing patient is re-established, IMP inhalation and follow-up should resume according to the protocol.

## 11 TREATMENT OF PATIENTS

### 11.1 Standard of Care Alone

Patients randomized to the control arm will receive only the Standard of Care regimen as prescribed by the treating physician and as described in [Section 9.4.2](#).

Any changes in Standard of Care treatment will be documented in the eCRF.

### 11.2 L-CsA plus Standard of Care

Patients randomized to the L-CsA arm will receive L-CsA 5 mg twice daily in addition to SoC as prescribed by the treating physician and as described in Section 9.4.2. L-CsA will be administered as 5mg/1.25 mL inhalation via the [CCI](#) for 48 weeks.

Any changes in Standard of Care treatment will be documented in the eCRF.

### 11.3 Concurrent Treatment or Medication

All participants randomized, whether enrolled in the L-CsA arm plus SoC arm or Standard of Care arm of this protocol, will receive standard of care therapies for the maintenance of their allograft. SoC includes maintenance immunosuppressive medication, prophylaxis against common opportunistic infections, and all other necessary medications and therapies for the optimal care of the patient. This also include vaccination against CoV-SARS 2. Changes to immunosuppression and use of azithromycin are also considered SoC. All changes in the concurrent treatment or medication will be administered according to site's standard of care.

#### 11.3.1 Immunosuppressive Medication

##### Maintenance Immunosuppressive Therapy

Maintenance immunosuppressive therapy including tacrolimus, a second agent such as but not limited to MMF or azathioprine, and a systemic corticosteroid such as prednisone as third agent. will be administered according to institutional standards. Dosages, dates of start and stop or change in dosage will be recorded on the respective eCRF.

Systemic tacrolimus doses should not need to be adjusted based on prior experience using aerosolized cyclosporine A. However, systemic tacrolimus doses should be adjusted based upon renal function. Should elevations of creatinine occur during the course of the trial by 30% from baseline at randomization, tacrolimus levels given systemically should be reduced by approximately 30% from baseline and levels should be followed and creatinine monitored according to standard protocols at the discretion of the Investigator.

In the event of renal insufficiency (creatinine > 2.5 mg/dL), the dose of oral tacrolimus may be reduced by 30% and the creatinine should be followed by subsequent monthly blood analyses. Alternatively, a switch from Calcineurin Inhibitor (CNI) to mTOR inhibitors should be considered and will be allowed.

### Augmentation or Change of Immunosuppression

Augmentation or change of immunosuppression/immunomodulation following randomization of the patient into the clinical trial must be recorded on the concomitant medication page in the eCRFs.

#### **11.3.2 Prophylaxis and Therapy of Infections**

All patients will receive standard infectious disease prophylaxis and therapy consisting of appropriately targeted antibiotics, antivirals and/or antifungals according to institutional standards. Dates of start and stop or change in dosage will be recorded on the respective eCRF.

#### **11.3.3 Azithromycin**

Patients receiving azithromycin prior to randomization (for prophylaxis or treatment of BOS) must be on a stable regimen for at least 4 weeks prior to randomization. These patients can continue to receive azithromycin during the clinical trial as deemed appropriate by the investigator.

#### **11.3.4 Other Medication**

All concurrent treatment or medications given within 30 days prior to Randomization and until Visit 10/EoS, will be recorded in the eCRF.

The use of any inhaled formulation of Cyclosporine A other than the IMP is strictly prohibited during the complete clinical trial period. Topical formulations (e.g., eye drops) containing CsA are allowed. Patients should not receive systemic Cyclosporine A at any time during Screening and Randomization. If medically indicated after Randomization, the treating physician can exchange Tacrolimus for systemic Cyclosporine A.

[figure not shown]
[figure not shown]
[figure not shown]
[figure not shown]
[figure not shown]
All inhaled medications, except investigational inhaled medications, are permissible during the trial and should be administered in the following order: inhaled bronchodilators, inhaled corticosteroids, inhaled antifungals/antibiotics, and then inhaled L-CsA. Spirometry must be performed without the use of bronchodilators (see [Section 12.1.1](#)) and preferably before but at least 2 hours after the last administration of inhaled antifungals/antibiotics.

To standardize spirometry across the two treatment arms, patients should not use short-acting bronchodilators (e.g., albuterol) within 2 hours prior to spirometry. Patients on scheduled Long-Acting Beta Agonists (LABAs) or Long-Acting Muscarinic Antagonists (LAMAs) should ideally have spirometry done at the same time of day following their scheduled dose. Patients have to note their use and timing of bronchodilators carefully.

#### **11.3.5 CCI**

CCI

CCI

## 12 ASSESSMENT OF EFFICACY

### 12.1 Methods and Timing of Efficacy Assessments and Analyses

#### 12.1.1 Spirometry

##### 12.1.1.1 [REDACTED] CCI [REDACTED]

For on-site spirometry each clinical trial site will be provided with a CCI [REDACTED] [REDACTED], which will stay on site. Clinical trial personnel at each site will be trained and certified on the use of protocol specific software installed on the CCI [REDACTED]. Spirometry will be measured according to American Thoracic Society (ATS)/European Respiratory Society (ERS) spirometry guidelines at each visit [Miller 2005a; Miller 2005b; Wanger 2005; Pellegrino 2005]. Three acceptable maneuvers will be obtained and the largest value for FVC and FEV1 will be recorded. The CCI [REDACTED] from the maneuver with the largest sum of FEV1 + FVC will be recorded. FEV1, FVC, and CCI [REDACTED] will be recorded in absolute terms. Centralized overread will be applied to all maneuvers obtained.

It is well known that spirometry relies on the cooperation between the patient and examiner and that the results obtained will depend on technical as well as personal factors. Therefore, all efforts will be undertaken to have a particular patient assessed by the same examiner. To reduce the variability of the results, the method should be standardized as far as possible.

#### Within-maneuver acceptability criteria:

Individual spirograms are acceptable if:

- They are free from artefacts
  - Cough during the first second of exhalation
  - Glottis closure that influences the measurement
  - Early termination or cut-off
  - Effort that is not maximal throughout
  - Leak
  - Obstructed mouthpiece
- They have good starts
  - Extrapolated volume < 5% of FVC or 0.15 L whichever is greater
- They show satisfactory exhalation
  - Duration of ≥ 6 seconds or a plateau in the volume-time curve or if the patient cannot or should not continue to exhale

#### Between-maneuver repeatability criteria:

After three acceptable spirograms have been obtained, apply the following test:

- The two largest values of FVC must be within 0.150 L of each other

- The two largest values of FEV1 must be within 0.150 L of each other

If both of these criteria are met, the test session may be concluded.

If both of these criteria are not met, continue testing until:

- Both of the criteria are met with analysis of additional acceptable spirograms  
or
- A total of eight tests have been performed (optional)  
or
- The patient cannot or should not continue

Save, as a minimum, three acceptable and repeatable maneuvers.

#### 12.1.1.2 CCI [REDACTED]

Each site will receive portable spirometers CCI [REDACTED]

[REDACTED] for patients to be used at all on-site and remote visits. Clinical trial personnel will be trained in the use of the CCI [REDACTED], patients will be trained by the clinical trial personnel in the use of the device at screening. Refresher training for patients will be provided at all subsequent clinic visits (and during remote visits, if required). The patient will receive written instructions on how to use the CCI [REDACTED] to perform spirometry correctly.

Spirometry on the CCI [REDACTED] should be performed using the same within and between maneuver criteria that would be applied during on-site spirometry testing as described above. The largest value for FVC and FEV1 will be recorded. The CCI [REDACTED] from the maneuver with the largest sum of FEV1 + FVC will be recorded. FEV1, FVC, and CCI [REDACTED] will be recorded in absolute terms. As a minimum, three acceptable and repeatable manoeuvres will be recorded.

To assist the clinical trial personnel and patient to achieve the spirometry within (acceptability) and between (repeatability) manoeuvre criteria described above (Miller 2005a; Miller 2005b; Wanger 2005; Pellegrino 2005), the CCI [REDACTED] will be programmed to give feedback. For example, if an individual spirogram did not meet the start of test criteria, the device will indicate to the patient there was a slow start of test.

Spirometry data stored on the CCI [REDACTED] device will be transmitted to a central database, via a GSM cradle from the patients home and be subject to centralized overread.

#### 12.1.1.3 General considerations

For the determination of eligibility at Screening, only spirometry data obtained with the CCI [REDACTED] spirometer will be used.

To standardize spirometry across the two treatment arms, patients should not use a short-acting bronchodilator (e.g., albuterol) 2 hours prior to spirometry. If patients are on scheduled LABAs or LAMAs then the time from last dose to spirometry should be consistent throughout the study.

Spirometry should ideally be performed before, or a minimum of 2 hours following the last inhalation of inhaled antifungals/antibiotics.

All inhaled medications, except investigational inhaled medications, are permissible during the trial and should be administered in the following order: inhaled bronchodilators, inhaled corticosteroids, inhaled antifungals/antibiotics, and then inhaled L-CsA.

Spirometry must always be performed before L-CsA inhalation.

#### 12.1.1.4 Onsite visits

On-site spirometry should be performed by blinded personnel.

At every visit, spirometry will be measured using the CCI [REDACTED] and the CCI [REDACTED] spirometers. Instructions for Use (including additional information on accuracy checks, cleaning of the device and further support) for both devices are available in the Study Manual. At least three acceptable and repeatable maneuvers on each device should be obtained at each visit.

At Visit 1, the spirometry at CCI [REDACTED] will only be performed using the CCI [REDACTED]

Sufficient rest between both spirometry sessions should be granted to the subject at the Investigator's discretion. For the CCI [REDACTED] spirometry session, procedures identical to those to be used at home will be followed.

#### 12.1.1.5 Remote visits

If patients cannot attend clinic visits due to COVID-19, remote visits using guided home spirometry may be performed (FEV1, CCI [REDACTED], and FVC) on the CCI [REDACTED] device. For remote visits, the clinical trial personnel will telephone the patient and guide them through performing spirometry on the CCI [REDACTED] device (for further assessments during remote visits, see [Section 14.2.8](#)).

Home spirometry should be scheduled around the same time as the usual clinic visits, whenever possible, to minimize the effects of circadian variation of lung function measurements.

In case measurements are not satisfactory after central overread, home spirometry may be repeated as close to the initially scheduled remote visit as possible.

#### 12.1.2 Progression of BOS

Due to the patchy distribution of affected areas in the pulmonary allograft, chronic rejection and BOS are not uniformly detectable by biopsy. This method has turned out to be too unspecific and harmful for routine diagnostic use. Therefore, non-invasive spirometry has been routinely

---

established using standardized airflow measurements which nowadays is used to determine FEV1 as a surrogate marker for the diagnosis of BOS, its classification and its control of progression.

Progression of BOS during the treatment period is defined as a decline of FEV1 of  $\geq 10\%$  or  $\geq 200$  mL from Baseline FEV1 and absolute decrease in FEV1/FVC of  $> 5\%$  that is confirmed by measurements that are taken with **CCl** spirometer at least 2 weeks apart OR worsening in BOS Severity grade OR Re-transplantation, OR Death from respiratory failure.

#### **12.1.3 Augmentation or Change of Immunosuppression**

Augmentation or change of immunosuppression/ immunomodulation must be recorded in the eCRFs.

#### **12.1.4 Re-transplantation**

Re-transplantation is defined as the date that a patient undergoes lung re-transplantation surgery. The reason for re-transplantation will be recorded. At the time of re-transplantation, the patient will be withdrawn from the study.

#### **12.1.5 Death**

If a patient dies during the clinical trial, the medical monitor should be contacted as soon as is feasible. The cause of death and a clinical summary will be requested.

#### **12.1.6 Acute Rejection and its Severity**

A patient with symptoms of a concomitant medical condition should be evaluated as clinically indicated. If a patient is diagnosed with acute rejection, the diagnosis should be recorded according to the following classification scheme. Any medications used to treat acute rejection should be recorded on the concomitant medication eCRF. The grade of acute rejection, airway inflammation, chronic airway rejection and chronic vascular rejection will be evaluated by the Investigator according to the revised working formulation for classification and grading of pulmonary allograft rejection [Stewart 2007] ([Table 6](#)):

**Table 6. Revised Working Formulation for Classification and Grading of Pulmonary Allograft Rejection**

A: Acute rejection	
Grade 0	None
Grade 1	Minimal
Grade 2	Mild
Grade 3	Moderate
Grade 4	Severe
B: Airway inflammation	
Grade 0	None
Grade 1R	Low grade
Grade 2R	High grade
Grade X	Ungradable
C: Chronic airway rejection – obliterative bronchiolitis	
0	Absent
1	Present
D: Chronic vascular rejection – accelerated graft vascular sclerosis	

“R” denotes revised grade to avoid confusion with 1996 scheme.

#### **12.1.7 Antibody-Mediated Rejection**

While less common in patients more than one-year post-transplant, if the treating physician makes the diagnosis of antibody-mediated rejection (AMR), this should be recorded in the eCRF. The diagnostic criteria and a working consensus definition established by the ISHLT with the aim of determining criteria for pulmonary AMR and establishing a definition should be used to support the diagnosis [Levine 2016]. See [Appendix III](#) for further information on Antibody-Mediated Rejection.

#### **12.1.8 Quality of Life Questionnaire (EQ-5D-5L)**

The EQ-5D-5L is a standardized measure of health status developed by the EuroQol Group in order to provide a simple, generic measure of health for clinical appraisal. Patients will be asked to manually complete the EQ-5D-5L at Visits 1, 4, 6, and 9/EoT and results will be entered into the eCRFs by site staff.

#### **12.1.9 Hospitalizations**

Hospitalizations for any reason other than a scheduled procedure should be regarded as serious adverse event and should be recorded in the eCRFs with admission date, discharge date, reason for admission, and additional diagnoses. If a patient requires mechanical ventilation for any reason other than a planned surgical procedure, dates of mechanical ventilation, and reason for mechanical ventilation should be recorded separately. A Hospitalization Discharge Summary may be requested by the Medical Monitor and shared with the DMC and/or AC.

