
	
measurements taken with CCI [REDACTED] spirometer at least 2 weeks apart.
 
Changes to standard of care are allowed at the investigator's discretion (e.g., changes in doses of immunosuppression, azithromycin, ATG, Photopheresis, leukotriene receptor antagonists, cytostatics, irradiation therapy). All changes to SoC must be recorded in the electronic case report form (eCRF).
 
All medically indicated procedures performed during the course of the clinical trial will be documented in the eCRFs.
 
For assessment of patient survival, overall mortality, BOS-related mortality and non-BOS-related mortality will be taken into account at any time throughout the clinical trial period.
 
Cumulative dose of immunosuppressants will be assessed throughout the Study for tacrolimus, MMF/equivalent, and corticosteroids.
 
Quality of Life will be assessed at Visits 1, 4, 6, and 9/End of Treatment (EoT) when patients have to complete the EQ-5D-5L Questionnaire. Absolute and relative change from baseline will be calculated.
 
Hospitalization will be assessed for overall number of days, days on regular ward, days in ICU, and days in ICU on ventilation.
 
Assessment of Safety:
 
Safety Assessments at every visit include: physical examination, vital signs, adverse event reporting, and clinical laboratory tests performed in the local labs at each clinical trial site.
 
Acute tolerability of IMP will be assessed by measuring spirometry before and CCI [REDACTED]
 
[REDACTED]

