#### Serious Adverse Event (SAE)

Each adverse event is to be classified by the Investigator as SERIOUS or NON-SERIOUS.

The International Conference on Harmonisation (ICH) of Technical Requirements for Registration of Pharmaceuticals for Human Use defines a serious adverse event as any adverse event occurring at any dose that results in any of the following outcomes:

- Death
- A life-threatening event (immediate risk of death at the time of the event)
- Inpatient hospitalization or prolongation of existing hospitalization
- A persistent or significant disability/incapacity
- A congenital anomaly/birth defect
- Other important medical event (Medical and scientific judgment should be exercised in deciding whether expedited reporting is appropriate in other situations, such as important medical events that may not be immediately life-threatening or result in death or hospitalization but may jeopardize the patient or may require intervention to prevent one of the other outcomes listed in the definition above. These should also usually be considered serious.)

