#### ***13.1.1.4 Serious Adverse Event (SAE) Reporting***

Any serious adverse events occurring

- between the first clinical trial procedure after obtaining informed consent and within 4 weeks after the completion of the EoT visit, whether or not considered related to the clinical trial treatment assignment  
or
- at any time after completion of the last follow-up and coming to the attention of the Investigator, if it is judged as related to the patient's participation in the clinical trial

**must be reported to CCI IMMEDIATELY, but within 24 hours upon knowledge**, as follows:

- Document the event in the eCRF within 24 hours of discovery
- Submit the SAE report by Fax or e-mail to a list of predefined recipients.
- Follow-up the SAE until the outcome is determined, providing periodic updates in the eCRF
- Provide any additional information if requested

Contacts of PPD are as follows:

PPD		PPD	
		PPD	

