#### ***13.1.1.4.4 Events not Regarded as Adverse Events/Serious Adverse Events***

The following events will be not regarded as AEs/SAEs:

- Pre-scheduled (before any trial-related activities commenced) hospitalizations/surgeries/interventions
- Trial endpoint-related worsening; this will be assessed in the endpoint analysis.

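### Protocol 12.1.9 and Section 13 disagree on whether an adverse-event-driven admission for a procedure scheduled during the trial is a serious adverse event

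*Protocol*

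**What the plan says.** Four places in the protocol bear on whether an admission is a serious adverse event (SAE).

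- **Section 12.1.9** (in the efficacy chapter): "Hospitalizations for any reason other than a scheduled procedure should be regarded as serious adverse event". The same sentence asks for admission and discharge dates, the reason for admission and further diagnoses. It sets no time limit on the scheduling and does not define a scheduled procedure.
- **Section 13.1.1.1, SAE definition:** the protocol "defines a serious adverse event as any adverse event occurring at any dose that results in any of the following outcomes", and one listed outcome is "Inpatient hospitalization or prolongation of existing hospitalization". Planned admissions are not excepted. The same section counts worsening of a pre-existing condition as an adverse event (AE).
- **Section 13.1.1.4.4** opens with "The following events will be not regarded as AEs/SAEs" and gives two items. The first is "Pre-scheduled (before any trial-related activities commenced) hospitalizations/surgeries/interventions". The second is "Trial endpoint-related worsening; this will be assessed in the endpoint analysis".
- **Section 13.1.1.4** requires reporting within 24 hours of SAEs occurring "between the first clinical trial procedure after obtaining informed consent and within 4 weeks after the completion of the EoT visit".

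The synopsis adds a hospital-day measure: "Hospitalization will be assessed for overall number of days, days on regular ward, days in ICU, and days in ICU on ventilation". SAP Section 15.3 tabulates serious treatment-emergent AEs by treatment group, with emergence counted from the date of randomization. No text cross-refers 12.1.9 to 13.1.1.4.4 or says which prevails, and the visible SAP does not settle the matter.

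**The concern.** Sections 12.1.9 and 13.1.1.4.4 both carve out planned admissions, but only the second says when the planning must have happened. A site that relies on 12.1.9 can leave out an admission that an AE caused, because the procedure had a date in the diary. A site that relies on Section 13 reports the same admission as serious.

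What is at stake is the seriousness classification. The AE should still be recorded in the eCRF either way. If it is not marked serious, it escapes the 24-hour report, is not considered for expedited reporting under Section 13.1.1.4.1, and does not appear in the serious-event tables. Protocol Section 15.5 gives an adequately sized safety database as the reason for the combined enrolment target, and SAP Section 15.1 plans no inferential safety analysis. The counts themselves are therefore the safety evidence.

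**Working it through.** The plan states no figure to reproduce, so the check is to put each kind of admission through each rule.

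| Admission | 12.1.9 | 13.1.1.4.4 and 13.1.1.1 | Result |
|---|---|---|---|
| A. Planned before trial activity began | Outside the SAE rule | Exempt | Agree |
| B. Unscheduled, resulting from an AE, not endpoint-related | SAE | Not exempt; serious | Agree |
| C. Elective, arranged during the trial, no AE | Outside the SAE rule | Not exempt, but not serious, as no AE led to it | Agree |
| D. Scheduled procedure arranged during the trial for a new or worsened condition that is an AE, not endpoint-related | Outside the SAE rule | Not exempt; serious | **Conflict** |
| E. Scheduled procedure arranged during the trial for endpoint-related worsening | Outside the SAE rule | Exempt under the second item | Agree |
| F. Unscheduled, for endpoint-related worsening | SAE | Exempt under the second item | **Conflict** |

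Row D is the point. A bronchoscopy with admission, arranged after enrolment for suspected infection, is an example. Row F is a separate conflict between the same two sections and should be settled in the same edit.

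The dividing line in 13.1.1.4.4 is the start of trial-related activity, not randomization. Admissions arranged between consent and randomization can therefore fall in row D as well. Those would affect SAE reporting, but they enter the serious treatment-emergent tables only if the event began on or after the randomization date.

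**Size per patient.** Inputs: 62 patients randomized (SAP Section 8.2); 1:1 allocation (Protocol Section 9.3); all randomized patients expected in the safety set (SAP Section 9.2.1).

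- Patients per arm: 62 / 2 = 31, approximately, since the actual split is not given.
- Shift in one arm's serious-event rate for each patient whose only serious event is of type D: 1 / 31 = 0.032, or 3.2 percentage points.

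The documents give no rate of elective admissions, so the number of such patients, and hence the total effect, cannot be calculated.

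**The case against.** The best defence is that 12.1.9 does not actually exempt anything. It says that unscheduled admissions are to be treated as SAEs and is silent on scheduled ones. It sits in the efficacy chapter, while Section 13 holds the SAE rules. On that view 12.1.9 only adds a presumption for unscheduled admissions, and Section 13 decides the rest. One could also read its reference to scheduling as meaning scheduled before the trial. Both readings are reasonable, and either would remove the row D conflict. However, no text states either one, and 12.1.9 omits the time limit that 13.1.1.4.4 includes. With approximately 43 centers, uniform harmonization cannot be assumed.

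Other parts of the defence stand and limit the point. A reader might infer any of the following, and the documents do not support them:

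- **That every admission planned during the trial is affected.** Falling outside 13.1.1.4.4 does not make an admission serious. Section 13.1.1.1 needs an AE that results in the admission (row C).
- **That planned rescue treatment or a re-transplant work-up is a clear example.** Where the cause is BOS worsening, the second item in 13.1.1.4.4 may exempt it, and the sections then agree (row E).
- **That hospital days are lost.** Hospitalization is a listed assessment at Visits 2 to 9 (Section 14.2.3) and Visit 10 (Section 14.2.5). Section 14 asks patients to report any hospitalization between visits, and the synopsis measure has no exclusion for scheduled procedures. SAP text after Section 14.2.5 is redacted, so a counting rule may exist there.
- **That the arms are affected unequally.** Treating staff know the allocation (Section 9.3.1), so this is possible, but nothing shows it.

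**Conclusion.** The inconsistency is real and narrow. It concerns admissions for procedures scheduled after trial activities began, because of a new or worsened condition that is an AE and not endpoint-related worsening. For these, 12.1.9 read literally and Section 13 give opposite answers, with consequences for 24-hour reporting and the serious-event tables. The primary endpoint is untouched.

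The figure of 3.2 points per patient assumes about 31 patients per arm and applies only to a patient with no other serious event. Section 13.1.1.4.5 makes every confirmed COVID-19 case an SAE, and 12.1.9 adds unscheduled admissions, so some patients with a type D admission will already be counted. Any total would rest on an assumed number of patients, and none is offered here. The correction is worth making because a stated rule can produce a wrong classification and the remedy is cheap.

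**What to change.** 1. In Protocol 12.1.9, limit the exception to admissions scheduled before any trial-related activity, and state that an admission resulting from an AE is assessed under 13.1.1.1.
2. In the same edit, reconcile 12.1.9 with the endpoint-worsening item in 13.1.1.4.4, so that unscheduled admissions for such worsening (row F) have one classification. Changing only the scheduling phrase would leave that conflict in place.
3. State in 12.1.9 that dates are recorded for all admissions, including scheduled ones, so that the synopsis hospital-day total does not depend on SAE status.
4. Before database lock, query admissions that were not reported as SAEs because they were scheduled. Check each against the date of scheduling and the underlying AE. The data review meeting in SAP Section 9.2 gives a natural deadline. SAP Section 8.2 already reports the number randomized, so for admissions that have already occurred this query is the step that corrects the data.

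The cost is a short wording change, a few more SAE forms and one data query.
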